## 15.0 CONFIDENTIALITY

The identity of participants enrolled in the postapproval study and the information contained in their study records will be kept confidential in accordance with this protocol and the Informed Consent and Medical Release Authorization forms.

To ensure confidentiality, each participant will be tracked via a unique participant identifier. Participant names and contact information will be stored separately from participant data. Confidentiality will be protected throughout the study period.

Although a third party study entity will have complete access to all study data, the participant's name and data will not be disclosed, except to the FDA, IRBs, or courts of law as needed. In those events, Mentor will also receive access. Also, pursuant to consents and medical records release authorizations, the participant's name (but not data) will be disclosed to the participant's physicians, as part of medical record collection required by this protocol. Additionally, the participant's Social Security number may be used to search proprietary databases (e.g., the National Change of Address (NCOA) database, the Social Security Death Index database, and other proprietary databases) as needed.

Data analyses and reports made available for review as required by the FDA and IRBs, will be reported as confidential statistical information.

Any research, presentations, and/or publications of study findings by Mentor, medical societies, or other third parties will not disclose participant names or other participant identifying information.

**16.0 FORMS**

Secondary Procedures/Reoperations  
Discontinuation Form

MENTOR	MGPAS Amendment 2		
 MGPAS Amendment 2 #085 Patient / Physician Information #001			
Participant No: 	Site No: 	Participant Initials: 	REOPERATION DataFax Code: 
DATE OF CONTACT			
Date of Contact:         DD MMM YYYY			
PATIENT INFORMATION			
Name (First, MI, Last): _____			
Date of Birth:      	Weight:      lb	SSN:      	
DD MMM YYYY			
Address: _____			
City, State, Zip Code: _____			
Country:  US  Canada		Phone Number: _____	
Cell Phone Number: _____		Fax Number: _____	
Email Address: _____			
PHYSICIAN INFORMATION			
Reporting Physician Name (First, MI, Last): _____ <small>(Principal Investigator)</small>			
Surgical Facility Address: _____			
City, State, Zip Code: _____			
Phone Number: _____		Fax Number: _____	
Email Address: _____			
Primary Care Physician Name (First, MI, Last): _____			
Address: _____			
City, State, Zip Code: _____			
Phone Number: _____		Fax Number: _____	
Email Address: _____			
V2 - 04FEB2015	Confidential CRF	Page 1	

MENTOR

MGPAS Amendment 2

  
MGPAS Amendment 2 #085 Reoperation (Page 1 of 3) #002

Participant No:   
Site No:   
Participant Initials:

**REOPERATION**  
DataFax Code:

**REOPERATION (Page 1 of 3)**

**PATIENT MEDICAL HISTORY**

**Breast Cancer Since Last Study Visit:**

**Breast or Chest Wall Radiotherapy Since Last Study Visit:**

Right Breast:  Yes  No

Right Breast:  Yes  No

Left Breast:  Yes  No

Left Breast:  Yes  No

**Medical Problems Since Last Study Visit:**  Yes  No

If YES, mark all that apply:

- Diabetes
- Thyroid Disease
- Liver Disease
- Renal Disease
- Cardiac Disease
- Hypertension
- Other, specify: \_\_\_\_\_

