**Figure 1**  
**PROTOCOL AMENDMENT 2 POST APPROVAL STUDY PROCESS FLOW CHART:**  
**MEMORYGEL PARTICIPANTS**

**Figure 2**  
**PROTOCOL AMENDMENT 2 POST APPROVAL STUDY PROCESS FLOW CHART:**  
**SALINE CONTROL PARTICIPANTS**

### **5.1 Participant Follow-up**

The study is currently in year 7 and follow-up will continue through 10 years or until the National Breast Implant Registry opens for data collection, whichever occurs first. At each follow-up contact, the following data will be collected:

- Updated participant and physician contact information
- Updated patient medical history
- Explantation and reoperation information
- Reasons for reoperation, with or without removal.

The surgeon/investigative site will submit the completed data collection forms via Internet or mail to a third party entity for entry into the study database

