#### Complications/Reoperations

The cumulative incidence of key local complications (explantation, and reoperation) for women with MemoryGel implants will be estimated based on physician evaluations for the MemoryGel participants using Kaplan-Meier methodology to estimate the time to the first occurrence of the complication or reoperation. Ninety-five percent confidence intervals will be computed. In addition, the relative frequency of reasons for reoperation will be computed.

Under the original protocol, the purpose of the inclusion of the saline participants was to serve as concurrent controls for assessing rheumatologic and neurologic signs. Rheumatological and neurological data will not be collected under this protocol amendment.

Mentor will generate the following final clinical study reports for submission to FDA:

- One final report at the end of the study phase conducted under Amendment 1, including data from beginning of the study through the end of the study phase under Amendment 1. The statistical analysis will be conducted as described in the original protocol (see below).
- One final report at the end of the study phase conducted under Amendment 2, including data from the execution of Amendment 2 to the end of the study. The statistical analysis will be conducted as described above.

The original analyses conducted to address each of the postapproval study's original objectives are identified below and correspond to issues outlined in Table 1:

*It is important to recognize that this study is observational. As a result, data from this study can be used only to establish association, not causality, and data should be evaluated within the context of the broader composite of literature relating to these issues. All of the analyses, except for the analyses of rheumatological and neurological signs and symptoms, will be based on the MemoryGel participants only.*

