#### **14.0 RE-CONSENTING OF PARTICIPANTS DISCONTINUED DUE TO PATIENT NON-COMPLIANCE**

To maximize the collection of re-operation data, participants discontinued due to patient non-compliance prior to this protocol amendment will be offered the opportunity to re-consent and re-establish participation.

Prior to this protocol amendment, a participant was considered discontinued due to patient non-compliance when the following criteria were met:

- If, within the past three (3) years, the patient has not completed an annual follow-up questionnaire per the study protocol either on-line, by mail, or by telephone; and
- If, within the past three (3) years, a Surgeons Local Complication Form pertaining to an in-person office visit by the patient per the study protocol has not been filed by the investigating physician.

If a participant discontinued due to patient non-compliance presents for re-operation or secondary procedure they should be informed by the investigator that the protocol has been amended and there is an option to re-consent.

Participants discontinued due to patient non-compliance who wish to voluntarily reinstate participation will be provided with the IRB approved Addendum to Informed Consent for review. The investigating physician or designee will conduct the informed consent discussion. If the patient agrees to reinstate participation the Addendum to Informed Consent form will be signed and dated by both the participant and person obtaining consent.

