**REOPERATION**

Date of Reoperation:   
*DD MMM YYYY*

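### The Amendment 2 reoperation form does not ask about earlier reoperations or removals, so an operation never reported to the study can make a later one look like the first

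*Combined protocol and SAP*

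**What the plan says.** Section 11.1 (Complications/Reoperations, Amendment 2 text) estimates the cumulative incidence of explantation and reoperation from physician evaluations, "using Kaplan-Meier methodology to estimate the time to the first occurrence of the complication or reoperation". The Amendment 2 final report is described as "including data from the execution of Amendment 2 to the end of the study". Section 5.1 gives the stage reached: "The study is currently in year 7 and follow-up will continue through 10 years", or until the national registry opens if that is sooner.

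The only Amendment 2 evaluation in Section 5.0 is the surgeon's report of a reoperation. Page 1 of the Reoperation form in Section 16.0 has three look-back items: breast cancer, "Breast or Chest Wall Radiotherapy Since Last Study Visit" and "Medical Problems Since Last Study Visit". It then takes a single "Date of Reoperation" for the operation being reported. No visible item asks whether there was an earlier reoperation or removal, or whether this is the first. The device fields on the next page describe only the replacement.

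Section 14.0 defines earlier discontinuation for non-compliance by two conditions that must both hold: "within the past three (3) years, the patient has not completed an annual follow-up questionnaire", and no surgeon complication form filed in the same period. Such women may re-consent when they present for a reoperation.

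**The concern.** A first-event analysis needs to know whether the operation in hand is the first. The form looks back for other history but not for the endpoint itself, and no other Amendment 2 source fills the gap. Section 3.0 ends scheduled visits and questionnaires, and Section 10.0 says that medical records will not be obtained. The Discontinuation form has no operation field.

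If an operation was never reported, the woman stays in the risk set after her true first event. Her next operation is then counted as the first, too late on the time axis. Removal and reoperation rates over time form one of the only two questions left in Section 2.0. Section 1.0 also calls the amended study a pilot for the registry, so the omission could be carried forward.

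**Working it through.** **Where an unreported operation can arise.** Under the Section 14.0 rule, a woman still active when Amendment 2 starts may have gone up to three years without contact. A re-consented woman has gone at least three. After that, contact occurs only at a reoperation that a study surgeon reports. Section 9.0 refers to participants' mobility and offers lists of other surgeons, so surgery elsewhere is plausible.

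**How many women lack recent follow-up.** Section 4.0 gives 21.8% follow-up through six years among 41,451 MemoryGel participants. 0.218 × 41,451 = 9,036, which leaves 32,415 without it. The documents do not say how many of these were discontinued for non-compliance or would re-consent.

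**Share of apparent first operations that follow an unrecorded one.** The plan states no figure to reproduce. The inputs below are assumptions: constant reoperation hazard *h*, gap of *g* years, independent events, and no gap operation reported. The share is then P = 1 − exp(−*h* × *g*).

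| *h* per year | *g* = 3 | *g* = 5 | *g* = 7 |
|---|---|---|---|
| 1% | 3.0% | 4.9% | 6.8% |
| 3% | 8.6% | 13.9% | 18.9% |
| 5% | 13.9% | 22.1% | 29.5% |

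**Sensitivity at *g* = 3.**
- Clustering: if the hazard after one reoperation is *r* times higher, the share is *r*P / (*r*P + 1 − P). For *h* = 3% and *r* = 2 this is 0.172 / (0.172 + 0.914) = 16%.
- Capture: if half of gap operations were reported and linked, with independent events, the share is 0.5P / (1 − 0.5P). This gives 1.5%, 4.5% and 7.5% for *h* = 1%, 3% and 5%.

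**Effect of simply not counting these women as events.** Take *h* = 3%, a 3-year gap, no capture and a further 3 years of observation. P = 0.0861, and the true 3-year first-event incidence is also 1 − exp(−0.09) = 8.61%.
- Form unchanged, *r* = 1: the observed figure is 8.61%, no bias in level.
- Form unchanged, *r* = 2: 0.914 × 8.61% + 0.0861 × (1 − exp(−0.18)) = 7.87% + 1.42% = 9.28% (from unrounded terms), about 8% too high in relative terms.
- Events dropped once the woman reports a gap operation: 0.914 × 8.61% = 7.87%, about 9% too low. Women with a gap operation who never present again stay in the denominator as event-free.

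On these assumptions, dropping the events does at least as much harm to the level as leaving the form alone.

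**The case against.** The strongest reply is that the study already holds most of what is needed. Section 5.0 says reoperation data were recorded under the original protocol, and every form carries a participant number and a date. A reader might infer from the form that every second or later operation will be analysed as a first. The documents do not support that, because an operation reported in either phase can be linked. For those operations the weakness lies in Section 11.1, which limits the Amendment 2 report to its own period and gives no rule on prior events. Nor is it right that no analysis rule could help; linkage repairs the recorded cases.

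A reader might also infer that any operation in a contact gap stays unknown. That goes too far. Surgeons had committed to record reoperations at unscheduled visits, and a filed form would itself have ended the gap as Section 14.0 defines it. What remains is mainly surgery by non-participating or non-reporting surgeons.

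The size is open to challenge too. The documents give no hazard, repeat-operation ratio or capture rate, so the 16% above is one assumed case and not a central estimate. The date of last contact is a minor matter, since the study database can supply it.

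These limits stand. They do not remove the defect, because an operation never reported leaves nothing to link.

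**Conclusion.** The concern holds for unreported operations only. For those women the form gives no means of learning that the operation is not the first, and the recorded first-event date is too late. With a hazard of 1% to 5% per year, independent events and no capture, about 3% to 14% of apparent first operations after a 3-year gap are affected. Longer gaps or clustering raise this; any capture lowers it. The range illustrates scale and is not an estimate from study data. The change is worth making because the error in timing has a known direction and the missing item is small.

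**What to change.** 1. **Form, history block (Section 16.0, Reoperation page 1).** Add: *Any breast reoperation or implant removal, by any surgeon, since [pre-printed date of last study contact]? Side, date, implant removed yes/no.*
2. **Section 11.1.** State that prior events are identified from the full study record of both phases, by participant number, plus this item; that time runs from implantation; and that the first event is dated by the earliest known operation. The full record is needed because a re-dated event may fall before Amendment 2 began and would drop out of a report limited to that period.
3. **Reporting.** Give the number of first events preceded by an operation known only from the new item, and show the curve with and without re-dating. Do not remove these women from the Amendment 2 event count as the primary rule, for the reason shown in the working.

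The cost is one line on a form already completed at the operation, a short addition to Section 11.1, and routine IRB notice of the form change. The item relies on recall and recovers gap operations only in women who present again. It improves the timing of the curve more than its 10-year level. It does not address the separate problem that re-consented women re-enter because they are having a reoperation.

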**REOPERATION**

Date of Reoperation:   
*DD MMM YYYY*

**Operation:**

Right: Left:

- None
- Replacement
- Explant Only
- Capsulectomy Only
- Other, specify: \_\_\_\_\_

**Capsulectomy:**

Right: Left:

- None
- Full Capsulectomy
- Partial Capsulectomy

MENTOR	MGPAS Amendment 2		
 MGPAS Amendment 2 #085      Reoperation (Page 2 of 3) #003			
Participant No: 	Site No: 	Participant Initials: 	REOPERATION
			DataFax Code:  
REOPERATION (Page 2 of 3)			
ADDITIONAL PROCEDURE INFORMATION - RIGHT			
Drains used?  Yes  No  Unknown			
If YES, was closed suction used?  Yes  No			
Acellular Dermal Matrix (ADM) used (ex. Collagen-mesh, etc.)?  Yes  No  Unknown			
Type, if known (human, porcine, bovine, synthetic, etc.): _____			
Brand Name: _____			
Were any other implantable devices or products implanted at this surgery?  Yes  No  Unknown			
Type, if known: _____			
Was fat grafting performed during this procedure?  Yes  No  Unknown			
ADDITIONAL PROCEDURE INFORMATION - LEFT			
Drains used?  Yes  No  Unknown			
If YES, was closed suction used?  Yes  No			
Acellular Dermal Matrix (ADM) used (ex. Collagen-mesh, etc.)?  Yes  No  Unknown			
Type, if known (human, porcine, bovine, synthetic, etc.): _____			
Brand Name: _____			
Were any other implantable devices or products implanted at this surgery?  Yes  No  Unknown			
Type, if known: _____			
Was fat grafting performed during this procedure?  Yes  No  Unknown			
REPLACEMENT DEVICE INFORMATION			
Right:	Left:		
	 None		
	 Mentor MemoryGel		
	 Mentor MemoryShape		
	 Mentor Saline, cc: _____	Manufacturer: _____	
	 Other silicone gel breast implant	_____	
	 Other saline breast implant, cc: _____	_____	
V1 - 14JAN2015		Confidential CRF	
		Page 3	

MENTOR	MGPAS Amendment 2		
 MGPAS Amendment 2 #085 Reoperation (Page 3 of 3) #004			
Participant No:	Site No:	Participant Initials:	REOPERATION
			DataFax Code: 
REOPERATION (Page 3 of 3)			
RIGHT		LEFT	
Mark ALL that apply	Mark ONE primary	Mark ALL that apply	Mark ONE primary
			 Not Done/Not Applicable
REASON FOR REOPERATION (Complication):			
			 Capsular Contracture, mark one Baker Grade:  Grade II
			 Grade III
			 Grade IV
			 Extracapsular Extravasation
			 Hematoma
			 Infection
			 Ptosis
			 Seroma
			 Skin Necrosis
			 Wound Problems
			 Wrinkling/Rippling
REASON FOR REOPERATION (Device Maintenance):			
			 Correction of Asymmetry
			 Device Migration
			 Implant Malposition
			 Suspected Rupture/Deflation
REASON FOR REOPERATION (Patient Request/Other):			
			 Patient wishes change in shape/size/style
			 Need for Biopsy
			 Staged Reconstruction
			 Tumor
			 Other, specify: _____
Reporting Physician (Principal Investigator) Signature			Date:    
			DD                  MMM                  YYYY
V2 - 04FEB2015	Confidential CRF	Page 4	

MENTOR	MGPAS Amendment 2												
 MGPAS Amendment 2 #085      Discontinuation #099													
Participant No:	Site No:	Participant Initials:											

 
  	 	 	 	
 
					
 
  	 	 	 	
 
					
 
  	 	 	
 
			
DISCONTINUATION													
Date of Discontinuation:													

 
  	 	 	
 
 DD                      MMM                      YYYY													
Reason for Discontinuation: (Mark one only)													
 Completed 10-year study													
 Consent withdrawn													
 Lost to follow-up													
 Death, cause of Death: _____													
 Other, specify: _____													
Principal Investigator's Signature	Date: 
 
  	 	 	
 
 DD                      MMM                      YYYY												
Principal Investigator's Printed Name													
V1 - 14JAN2015	Confidential CRF	Discontinuation
